ketoacidosis and growth attenuation have been reported in pediatric T1DM patients on a VLCD¹³, therefore, we anticipate low rates of these adverse events with the LCD intervention.

Aim 2 will provide preliminary estimates of the change in the atherogenic lipoprotein profile in patients on a LCD versus SCD. The primary outcome measure will be change in total LDL-P from baseline to 12 weeks after the nutrition intervention. As secondary outcomes, we will measure the change in other contributors to atherogenic lipoprotein load, such as high-density lipoprotein particle (HDL-P) number, small LDL-P number, and LDL size.

Aim 3 will provide preliminary estimates of the change in QOL in patients on a LCD versus SCD. Participants will complete the PedsQL, a validated QOL measure in T1DM patients, and Problem Areas in Diabetes-Teen (PAID-T), a validated measure of diabetes-specific distress, at baseline (week 0) and at 12 weeks after the nutrition intervention^{31,32}. Additionally, parents of participants will complete the WHO-5 Well-Being Index, a questionnaire for assessing subjective psychological well-being³³, and Problem Areas in Diabetes-Parent Revised version (PAID-PR), a validated measure of perceived parental burden associated with caring for a child with diabetes.³⁴

We will perform an independent samples t-test to compare outcomes between groups, in addition to multilinear regression analysis to account for potentially confounding covariates, such as total daily dose of insulin, weight change, glycemic variability as measured by continuous glucose monitoring (CGM), and age.

This proposed research will be the first prospective study to determine the effect of a LCD intervention on key diabetes outcomes in a pediatric T1DM population. This study will also provide a basis of training for a new pediatric investigator in the conduct of clinical trials under the mentorship of a highly successful mentorship team including [name] and [name].

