6.1.1 Study Visit 1, Initial Screening Visit (Week -2)

Screening visits will take place in a room designated for research in the Eskind Diabetes Center or the Vanderbilt Children's Endocrinology Franklin Clinic.

The purpose of the screening visit is to:

- obtain informed, written consent/assent,
- conduct a history and physical exam,
- confirm each participant is able to properly use their insulin pump and continuous glucose monitor (CGM),
- calculate the estimated energy requirement to be consumed before during the study period,
- show participants how to log their food intake on their digital device.

The screening visit will consist of the following:

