6.1.1.6 Randomization

We will then randomize patients to 1 of 3 groups: group 1 is low carbohydrate diet, group 2 is standard carbohydrate diet, group 3 is general diabetes education without dietary recommendation. Each group will contain 15 participants. Random permuted blocks with a fixed size of 3 will be used for randomization into treatment groups.

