6.1.2 Run In Period (Weeks -2 to 0)

Participants will log all dietary intake in the smartphone nutritional tracking app, which will serve as a baseline of dietary habits. They will also be instructed to consistently wear the CGM and to administer insulin boluses using their pump's bolus calculator.

Participants in groups 1 and 2 will be asked to complete nutritional tracking in the smartphone app during this time. Participants in group 3 will be asked to complete a blood sugar and exercise log.

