6.1.3.2 Blood draw

Blood will be drawn from each participant and the following labs obtained:

- HbA1c
- Beta hydroxybutyrate
- NMR spectroscopy lipoprofile.

6.1.3.3 Continuous glucose monitor and insulin pump data collection

Continuous glucose monitor and insulin pump will be downloaded into a HIPAA and FDA-compliant cloud-based, data-integration platform such as Dexcom Clarity, Medtronic Carelink, or Tidepool.

Information that will be collected from the continuous glucose monitor download will include (but not be limited to):

- Percent of time spent above the glycemic target of 140 mg/dL
- Percent of time spent in the glycemic target of $70-140\,$ mg/dL
- Percent of time spent below the glycemic target of 70 mg/dL
- Percent of time spent in hypoglycemia below 50 mg/dL
- Average blood glucose
- Blood glucose standard variation

Information that will be collected from the insulin pump download will include (but not be limited to):

- Average total daily dose of insulin
- Average bolus amount of insulin per day
- Average basal amount of insulin per day

6.1.3.4 Nutritional tracking smartphone application data collection

Information that will be collected from the smartphone app will include (but not be limited to):

- Total number of calories consumed
- Average grams of carbohydrates consumed per day
- Average grams of fat consumed per day
- Average grams of protein consumed per day
- Additional macronutrient data

Participants will also be asked to photograph all food consumed in the 24 hours prior to the study visit. At the study visit, they will complete a 24 hour dietary recall.

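### Baselines for the HbA1c, LDL-P and quality-of-life change scores are first taken two weeks after randomization, with no step withholding the allocation until then; the self-reported surveys are most exposed

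*Combined protocol and SAP*

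**What the plan says.** **Allocation.** Randomization is the last step listed under Visit 1, which is set at week -2 (section 6.1.1.6): "We will then randomize patients to 1 of 3 groups: group 1 is low carbohydrate diet, group 2 is standard carbohydrate diet".

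**Run-in, weeks -2 to 0.** Section 6.1.2 opens with a task for everyone: "Participants will log all dietary intake in the smartphone nutritional tracking app, which will serve as a baseline of dietary habits". It then splits the task by arm: "Participants in groups 1 and 2 will be asked to complete nutritional tracking in the smartphone app during this time", whereas "Participants in group 3 will be asked to complete a blood sugar and exercise log". Section 6.1.1.4, also under Visit 1, adds a manual glucose log for group 3 only.

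**Baseline, Visit 2, week 0.** Section 6.1.3.2 states: "Blood will be drawn from each participant and the following labs obtained"; the list includes HbA1c and the NMR lipoprofile. The participant and parent surveys follow in section 6.1.3.5, in line with Aim 3 in section 2.0, which times them "at baseline (week 0) and at 12 weeks after the nutrition intervention". The diet instructions come after these, in section 6.1.3.6.

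**Analysis.** Section 10.2 compares change from baseline in HbA1c, LDL-P and QOL score by t-test, and uses the same changes as dependent variables in regression. The regression covariates are insulin dose per body mass, weight change, CGM coefficient of variation and age. The baseline value of the outcome is not among them.

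The only HbA1c sought before allocation is the most recent value asked for at first contact (section 5.1.2), which is a screening item. No section describes keeping the assignment from families until week 0.

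**The concern.** A baseline should be a value that the allocation cannot have touched. Here each analysed baseline is recorded after allocation, at a time when the family may know the arm.

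The surveys are the main worry. Adolescents and parents rate well-being and diabetes distress themselves, and anticipation, worry or disappointment about the assigned arm could colour those answers at week 0 and fade later. The plan expects QOL differences between diets to be minimal (section 2.0), so a modest transient shift could create or hide the finding of interest.

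The run-in diet log is affected in another way. It is meant to describe habitual intake but is recorded after allocation, so it cannot show whether families told to expect low carbohydrate had already begun to change. It is not one of the change scores in section 10.2, so it introduces no bias there directly.

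**Working it through.** **1. The plan's own figure.** Section 10.1 gives a minimum important difference of 0.3% in HbA1c change and a pooled SD of 0.8%. So d = 0.3/0.8 = 0.375, stated as 0.38, which reproduces. The point does not depend on it.

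**2. Gap between allocation and baseline.** Week 0 − (week -2) = 2 weeks. Section 5.4 labels Visit 2 as week 1, which would give 1 − (−2) = 3 weeks. The two labels need reconciling.

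**3. Who can know the arm during the run-in.** Group 3 can, because its log differs. Groups 1 and 2 share one task, so the task does not separate low from standard carbohydrate. For that contrast, disclosure is inferred from the absence of any concealment step.

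**4. Effect on a change score.** Let δ be the true between-arm difference in 12-week change, b the between-arm difference in baseline caused by knowing the arm, and k the fraction of b still present at week 12.

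- Expected estimate = δ + k·b − b = δ − (1 − k)·b.
- If the shift has gone by week 12 (k = 0), the estimate is off by the full b.
- If the shift persists entirely (k = 1), it is not off at all.

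The documents give neither b nor k, so size and direction are unknown.

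**5. Would baseline adjustment cure it?** It is not planned. If it were added, the estimate would be δ + k·b − β·b, where β is the slope of the week-12 value on the week-0 value. With equal variances β equals the correlation r. With k = 0 the error left is r·b: half of b at an assumed r = 0.5, and 80% of b at an assumed r = 0.8. Adjustment reduces the error but does not remove it.

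**6. HbA1c with an early start.** Take 0.30 as the 12-week effect, as section 10.1 defines it, and assume linear accrual.

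- Rate: 0.30/12 = 0.025 per week.
- Gained by week 0, starting at week -2: 2 × 0.025 = 0.05.
- Gained by week 12: 14 × 0.025 = 0.35.
- Measured change: 0.35 − 0.05 = 0.30.

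Nothing is lost; this is the k = 1 case of step 4. A loss needs the effect to slow or level off before week 12, and also needs participants to change their diet before being taught it. No figure for LDL-P can be derived from the documents.

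**7. Scale.** Taking 0.8 as the SD of change, the standard error of a two-arm difference is 0.8 × √(2/n). This is 0.25 at n = 20 (section 10.1) and 0.29 at n = 15 (section 6.1.1.6).

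**The case against.** The best case for the plan has four parts.

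- Nothing says that families are told their arm at Visit 1. The listed purposes of that visit mention neither randomization nor disclosure, and the timeline figure could not be read.
- The arm-specific logs reveal only group 3, while the aims and the minimum important difference concern low versus standard carbohydrate, and section 10.2 compares two groups.
- Diet teaching is listed after the blood draw and the surveys, with the diet running from week 0, so HbA1c and lipoproteins have little reason to move beforehand.
- This is a pilot giving preliminary estimates, and a standard error of 0.25 to 0.29 would swamp a small HbA1c shift.

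All four stand as limits on the point. They do not change the order of events, and they do not protect surveys answered by families who may already know the arm. A shift tied to the arm also does not average out as sampling error does.

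Two stronger readings are tempting. A reader might infer that two run-in weeks out of 14 put 2/14 = 14% of the HbA1c effect into the baseline, so that 0.30 would appear as 0.30 × (1 − 2/14) = 0.26. That treats 0.30 as a 14-week effect, whereas the plan defines and analyses a 12-week change; step 6 of the working shows no loss. A reader might also infer that an openly known allocation is stated in the plan. It is not; for the two diet arms it rests on silence.

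**Conclusion.** The point holds as a sequencing weakness across all three aims, and chiefly for the self-reported outcomes of Aim 3. Baselines follow allocation by two weeks on the section 6.1 timetable, no concealment is described, and the analysis is change from those baselines.

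For the surveys, the bias in the between-arm change equals whatever arm-related baseline shift has faded by week 12. The documents do not allow a value or a sign to be put on it, and it may be zero.

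For HbA1c and LDL-P the risk is smaller, and no attenuation figure should be quoted.

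The conclusion assumes that families may learn the arm at or soon after Visit 1. If the assignment is in practice withheld until after the week 0 measures, what remains is that the protocol does not say so and that the run-in logs give group 3 away. This is a cheap improvement.

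**What to change.** Move section 6.1.1.6 to Visit 2: after the run-in review, blood draw, downloads and surveys (through section 6.1.3.5) and immediately before section 6.1.3.6. If randomization must stay at Visit 1, state that the assignment is not disclosed to participant or family until that same point.

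In section 6.1.2, give all participants one common run-in logging task. This also settles that section's conflict over who logs diet. In sections 6.1.1.4 and 6.1.2, start the group 3 glucose and exercise logs only after allocation.

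The surveys can then stay at week 0, as Aim 3 requires. Moving them to Visit 1 instead would conflict with Aim 3 and give a 14-week survey interval against 12 weeks for the blood outcomes. If randomization itself moves, the run-in exclusions in section 6.1.3 also fall before allocation.

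Cost: every participant, including those later assigned to group 3, keeps the same two-week log; allocation and diet planning have to be done at Visit 2; and group-specific instructions move from Visit 1 to Visit 2. The sample size does not change, and the gap between allocation (or its disclosure) and baseline falls from 2 weeks to 0.

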6.1.2 Run In Period (Weeks -2 to 0)

Participants will log all dietary intake in the smartphone nutritional tracking app, which will serve as a baseline of dietary habits. They will also be instructed to consistently wear the CGM and to administer insulin boluses using their pump's bolus calculator.

Participants in groups 1 and 2 will be asked to complete nutritional tracking in the smartphone app during this time. Participants in group 3 will be asked to complete a blood sugar and exercise log.

6.1.3 Study Visit 2 (Week 0)

This visit will correspond with the participant's routine diabetes follow up at the Eskind Diabetes Center or Vanderbilt Children's Endocrinology Franklin clinic with their primary endocrinologist. Each T1DM participant's endocrinologist will manage his or her glycemic control and insulin doses throughout the study. The study team will review data from the nutrition log, CGM, and insulin pump. Participants will be excluded for any of the following:

- Tracking < 2 meals per day in the nutritional tracking app
- Entering carbohydrates from < 2 meals per day in their insulin pump
- Wearing CGM < 80% of run-in period.

6.1.3.1 History and Physical Exam

The PI or designee will review each subject's clinical history, perform a physical exam, and take anthropometric measurements. They will ensure the patient has an up to date intramuscular glucagon kit for treatment of hypoglycemia as needed.

6.1.3.2 Blood draw

Blood will be drawn from each participant and the following labs obtained:

- HbA1c
- Beta hydroxybutyrate
- NMR spectroscopy lipoprofile.

6.1.3.3 Continuous glucose monitor and insulin pump data collection

Continuous glucose monitor and insulin pump will be downloaded into a HIPAA and FDA-compliant cloud-based, data-integration platform such as Dexcom Clarity, Medtronic Carelink, or Tidepool.

Information that will be collected from the continuous glucose monitor download will include (but not be limited to):

- Percent of time spent above the glycemic target of 140 mg/dL
- Percent of time spent in the glycemic target of $70-140\,$ mg/dL
- Percent of time spent below the glycemic target of 70 mg/dL
- Percent of time spent in hypoglycemia below 50 mg/dL
- Average blood glucose
- Blood glucose standard variation

Information that will be collected from the insulin pump download will include (but not be limited to):

- Average total daily dose of insulin
- Average bolus amount of insulin per day
- Average basal amount of insulin per day

6.1.3.4 Nutritional tracking smartphone application data collection

Information that will be collected from the smartphone app will include (but not be limited to):

- Total number of calories consumed
- Average grams of carbohydrates consumed per day
- Average grams of fat consumed per day
- Average grams of protein consumed per day
- Additional macronutrient data

Participants will also be asked to photograph all food consumed in the 24 hours prior to the study visit. At the study visit, they will complete a 24 hour dietary recall.

6.1.3.5 Quality of life survey

Participants will complete the PedsQL, a validated QOL measure in T1DM patients, and Problem Areas in Diabetes-Teen (PAID-T), a validated measure of diabetes-specific distress^{31,32}. They will also

complete the Self-Care Inventory, a validated measure of adherence with diabetes self-care behaviors³⁵. All surveys will be scored by a member of the research team.

Additionally, parents of participants will complete the WHO-5 Well-Being Index, a questionnaire for assessing subjective psychological well-being³⁴, and Problem Areas in Diabetes-Parent Revised version (PAID-PR), a validated measure of perceived parental burden associated with caring for a child with diabetes³³. All surveys will be scored by a member of the research team.

6.1.3.6 Diet Instructions

From weeks 0 to 12, research participants in groups 1 and 2 will consume a weight-maintaining diet designed by the Vanderbilt Diet, Body Composition, and Human Metabolism Core and the research team.

The research team will discuss food preferences with each participant to design diet plan with standard macronutrient contents. The Institute of Medicine formula⁷ or similar formula will be used to calculate the estimated energy requirement (EER).

EER for males (kcal/day) = $662 - (9.53 \times \text{age [y]}) + \text{PA} \times (15.91 \times \text{weight [kg]} + 539.6 \times \text{height [m]}).$

Where PA is the physical activity coefficient:

PA = 1.00 if PAL is estimated to be \geq 1.0 < 1.4 (sedentary)

PA = 1.11 if PAL is estimated to be \geq 1.4 < 1.6 (low active)

PA = 1.25 if PAL is estimated to be \geq 1.6 < 1.9 (active)

PA = 1.48 if PAL is estimated to be \geq 1.9 < 2.5 (very active)

[figure not shown]
EER for females (kcal/day) = $354 - (6.91 \times age [y]) + PA \times (9.36 \times weight [kg] + 726 \times height [m])$

Where PA is the physical activity coefficient:

PA = 1.00 if PAL is estimated to be \geq 1.0 < 1.4 (sedentary)

PA = 1.12 if PAL is estimated to be \geq 1.4 < 1.6 (low active)

PA = 1.27 if PAL is estimated to be \geq 1.6 < 1.9 (active)

PA = 1.45 if PAL is estimated to be \geq 1.9 < 2.5 (very active)

Figure 2: Macronutrient Content of SCD and LCD

The study team will devise two isocaloric diet plans for each participant in groups 1 and 2. One plan, the standard carbohydrate diet (SCD), will reflect the acceptable macronutrient distribution range of the Institute of Medicine's Recommendations for Nutrition: carbohydrate (45%–65% of energy), protein (10%–30% of energy), and fat (25%–35% of energy) (figure 2).⁷ The other plan, the low carbohydrate diet (LCD), will reduce the percent caloric intake from carbohydrates and replace that amount with calories from dietary fat. Thus with the LCD, 45%–65% of energy will come from fat, 10-30% of energy will come from protein, and 25%–35% of energy will come from carbohydrates (figure 2).

Group 3 will serve as a control that receives the same number of education sessions as groups 1 and 2 to teach general diabetes management but without specific dietary recommendations. This study design will allow for discrimination of the effect of the composition of the diet versus the effect of receiving any nutritional prescription.

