6.1.1.4 Continuous Glucose Monitor Instructions

The study team will instruct T1DM participants in the use of a continuous glucose monitor (CGM) such as Dexcom G6 or Medtronic Guardian for the monitoring of glycemia during the study. The team will then show T1DM participants how to upload CGM data into a HIPAA and FDA-compliant cloud-based, data-integration platform such as Dexcom Clarity or Tidepool. The team will show the control participants how to use the CGM device during this time.

Participants in group 3 will also be asked to keep a manual blood glucose log intermittently throughout the study.

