6.1.4.2 Text Messaging

Participants will receive text messages 2 to 4 times per week³⁶ that will provide reminders regarding key components of the dietary intervention, encouragement regarding diabetes management, and general positive quotes. The study team will create a bank of 50 text messages for each dietary intervention (LCD and SCD), and participants will receive 2 to 4 of these text messages per week. Examples of message content include: "Try a breakfast high in protein! An omelet with a side of bacon would be a great choice" and "The only way of finding limits of the possible is by going beyond them and into the impossible – Arthur C. Clarke." The text message will be sent using the text messaging feature in RedCap with the Twilio messaging service and will contain no protected health information. Text messaging will continue until participants have completed study visit 3.

6.1.5 Telephone Visits (Weeks 2, 4, and 8)

The study team will monitor adherence by reviewing each participant's dietary log, CGM data, and insulin pump data. The team will conduct a 30 to 60-minute telephone session (either via Facetime, Skype, or phone call) with the participant. The study team will review with the participants their nutritional intake and reinforce key concepts from the diet to which they are assigned (LCD or SCD). If the CGM is being worn less than 80% of the time or insulin pump is not being used to record more than 2 meals per day, the study team will troubleshoot the reason for suboptimal adherence with the participant.

Participants in groups 1 and 2 will be asked to complete nutritional tracking in the smartphone app during this time. Participants in group 3 will be asked to complete a blood sugar and exercise log.

In the event that study visit 3 occurs more than 14 weeks after study visit 2, we will conduct an additional telephone visit at week 12. We will

continue to conduct a telephone visit every 4 weeks after week 12 until the participant has completed study visit 3.

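### Groups 2 and 3 differ in more than the dietary prescription, so SCD versus group 3 compares two packages and cannot isolate the effect of a prescription

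*Combined protocol and SAP*

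**What the plan says.** Section 6.1.1.6 defines the third arm: "group 3 is general diabetes education without dietary recommendation". Section 6.1.3.6 adds: "Group 3 will serve as a control that receives the same number of education sessions as groups 1 and 2 to teach general diabetes management". The same section, and section 2.0 before it, draws the inference: "This study design will allow for discrimination of the effect of the composition of the diet versus the effect of receiving any nutritional prescription".

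Self-monitoring differs by arm. Section 6.1.1.4 states: "Participants in group 3 will also be asked to keep a manual blood glucose log intermittently throughout the study". For the run-in (6.1.2), the telephone visits (6.1.5) and the week 12 visit (6.1.6.4), the plan says of the diet arms: "Participants in groups 1 and 2 will be asked to complete nutritional tracking in the smartphone app during this time". Of the control arm it says: "Participants in group 3 will be asked to complete a blood sugar and exercise log".

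Section 6.1.4.2 sends text messages to participants in general, but the content is prepared by diet: "The study team will create a bank of 50 text messages for each dietary intervention (LCD and SCD". Section 6.1.5 describes the telephone sessions as reinforcing the assigned diet, LCD or SCD, and gives no content for group 3.

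**The concern.** LCD versus SCD addresses diet composition. The effect of having a prescription at all can only come from a comparison with group 3, most naturally SCD versus group 3. For that contrast to carry the claimed meaning, the two arms should be alike except for the prescription. They are not: group 3 has its own curriculum and its own logging task, and group 2 has food tracking and diet-specific messages.

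The stake is interpretation. If SCD and group 3 end with similar HbA1c changes, sections 2.0 and 6.1.3.6 invite the conclusion that a prescription does nothing. The same result would arise if both packages helped equally. A difference would be just as ambiguous, because it could come from food tracking and not from the plan that was prescribed. Section 10.1 says that the pilot's estimates are meant to inform a definitive trial, so a misread contrast could carry forward.

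**Working it through.** **Step 1. Set the two arms side by side.**

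| Component | Group 2 (SCD) | Group 3 | Sections |
|---|---|---|---|
| Diet plan | Prescribed | None | 2.0, 6.1.3.6 |
| Number of education sessions | Same | Same | 2.0, 6.1.3.6 |
| Session topic | Assigned diet | General diabetes management | 2.0, 6.1.1.6, 6.1.3.6, 6.1.5 |
| Self-monitoring task | Food tracking app | Blood sugar and exercise log; food tracking unclear (step 2) | 6.1.1.4, 6.1.2, 6.1.5, 6.1.6.4 |
| Text-message bank | Described | None described | 6.1.4.2 |
| Telephone content | Reinforces assigned diet | None described | 6.1.5 |
| CGM and pump instruction, device data review | Same | Same | 6.1.1.4, 6.1.1.5, 6.1.3, 6.1.4.1 |

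Besides the prescription, the arms differ in session topic, self-monitoring task, and described text and telephone content. The number of contacts is matched; their content is not.

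**Step 2. Check how firm each difference is.** The blood sugar and exercise logs are asked of group 3 only, in every place they appear. Food tracking is less clear. Section 6.1.1.3 asks participants generally to track intake. Section 6.1.2 first has all participants log their diet and then assigns food tracking to groups 1 and 2 and a different log to group 3. Section 6.1.3 excludes anyone tracking fewer than two meals a day in the app, without naming a group. Sections 6.1.5 and 6.1.6.4 again split the task by arm.

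**Step 3. Check timing.** Randomization is at the screening visit, week -2 (6.1.1.6). The logs start in the run-in (6.1.2), and baseline HbA1c is drawn at week 0 (6.1.3.2). The arm-specific tasks therefore begin before the baseline measurement.

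**Step 4. Write the contrast.** Assume that effects add. Let p be the HbA1c reduction due to the prescription, a the reduction due to group 2's other components, and b the reduction due to group 3's own components. Then:

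SCD versus group 3 = p + a − b, so the bias is a − b.

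The documents give no value for p, a or b. For illustration, take p = 0.3 percentage points, which borrows the size of the minimum important difference in section 10.1 (defined there for LCD versus SCD), and let a and b each range from 0 to 0.3:

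- a = 0 and b = 0, 0.1, 0.2, 0.3: the contrast shows 0.3, 0.2, 0.1, 0.0.
- b = 0 and a = 0.3: the contrast shows 0.3 + 0.3 = 0.6.
- a = b: the contrast shows 0.3, with no bias.

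**Step 5. Compare with the precision available.** The 95% half-width is t(0.975, 2n − 2) × SD × √(2/n), with SD 0.8 from section 10.1.

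- n = 15 per group (section 2.0): 0.8 × √(2/15) = 0.292; × 2.048 = ±0.60.
- n = 9 per group (15 × 0.6, after the 40% dropout allowed for in section 10.1): 0.8 × √(2/9) = 0.377; × 2.120 = ±0.80.

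A bias of up to 0.3 in either direction lies well inside these intervals, so the data could neither reveal it nor correct for it.

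**The case against.** Matching the number of sessions and filling them with non-dietary content is a recognised attention control, and a substitute log gives group 3 a comparable task. Diabetes-management content is not exclusive to group 3 either: all participants get device instruction, data review and their own endocrinologist's care, and the texts include "encouragement regarding diabetes management, and general positive quotes". One may also read the prescription as including its delivery, so that diet texts and telephone reinforcement belong to it. Section 10.2 compares only two groups and specifies no test of SCD against group 3. With a half-width of ±0.60, no conclusion of no effect would be safe even with perfectly matched arms.

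Much of this stands. It means that no specified analysis is damaged and that the fault lies in a claimed interpretation. It does not rescue the claim: even on the wide reading of prescription, group 3's curriculum and logs remain on the other side of the contrast.

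A reader might go further and infer that group 3's components lower HbA1c and so mask a real prescription effect. The documents do not support that. They attribute no HbA1c effect to the teaching or the logs. An intermittent manual log may add little when everyone wears CGM throughout (7.1.2). Group 2's food tracking and diet messages could push the contrast the other way. The 0 to 0.3 range is assumed, and its top was chosen to equal the protocol's own minimum important difference, so the apparent cancellation is built in.

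**Conclusion.** The statement in sections 2.0 and 6.1.3.6 claims a property that the design does not have. SCD versus group 3 compares a dietary-prescription package with a general diabetes-education package. The bias relative to a pure prescription effect is a − b, whose size and sign cannot be obtained from the documents; the figures in step 4 show scale under stated assumptions and are not estimates.

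LCD versus SCD, the contrast behind the three aims and section 10.1, is unaffected, because groups 1 and 2 share the same tasks and forms of contact. The conclusion rests on reading the arm descriptions as complete. If group 3 also tracks food, or receives texts and calls of similar form, the difference narrows, but the session topic and the two logs still separate the arms.

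**What to change.** 1. In sections 2.0 and 6.1.3.6, replace the claim with a statement that group 2 versus group 3 compares a dietary-prescription package with a general diabetes-education package matched on number of sessions. Add that it does not isolate the prescription, and that a null difference must not be read as showing that a prescription has no effect. This costs only wording.

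2. Reconcile sections 6.1.1.3, 6.1.2 and 6.1.3 with 6.1.5 and 6.1.6.4 on whether group 3 tracks food, and state to whom the run-in food-tracking exclusion applies. State also what text and telephone content group 3 receives. This too is wording.

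3. Optionally, make the self-monitoring tasks the same in all arms. This adds participant burden, in a trial that already allows for up to 40% dropout, so it is a trade-off for the investigators. Dropping group 3's log alone would not be enough: the session topics would still differ, and group 3 could be left with no tracking task. The rewording in item 1 is needed unless session topic and messages are aligned as well.
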